### **STUDY PROCEDURES:**

This study will be conducted at the University of Utah and the VA Medical Center. Information collected at the VA will be stored at the VA. For purposes of statistical analysis the information from the VA will be de-identified and sent to the University of Utah.

All patients will have a complete blood count, comprehensive biochemical profile (including serum calcium), thyroid-stimulating hormone (TSH), tissue transglutaminase antibody (TTG), C- reactive protein, and stool examination for electrolytes (optional), ova and parasite, C.difficile toxin (not required if stool is formed), Calprotectin or lactoferrin, and Giardia antigen. These tests will not be repeated if they were collected in the last 6 months. Blood and stool samples will be collected for storage if the patient consents. Flexible sigmoidoscopy and biopsy of the colonic mucosa will be performed in all patients at the beginning of treatment. Patients with red flag symptoms (onset in older than >50 years, progressive or non-fluctuating symptoms, unexplained weight loss, rectal bleeding or anemia, family history of colon cancer, fever, abnormal examination or laboratory tests) will have colonoscopy and biopsy. Patients with structural, biochemical, or infective disorders will be excluded from the study. A flexible sigmoidoscopy or colonoscopy will not be done if an acceptable biopsy was completed within 5 years. If the procedures are done a biopsy will be collected for storage.

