#### *Treatment Schedule*

This study will compare mesalamine two (Lialda®) 1.2 gm tablets orally daily to placebo in 68 patients with diarrhea predominant PI-IBS. The patients will be consented and enter into the screening which can last up to 8 weeks. This will be followed by an 8 week treatment period.

Patients will be re-consented to the newest version of the consent form if changes have been made while they are enrolled on the study. The patient may not be rescreened if there is no change in patient's symptoms if they are outside the screening window.

All patients will fill out the following questionnaires:

- 1) The Bowel Symptom Scale (BSS) at the beginning, at 4 weeks and at the end of the study period to assess any change based simply on admission to the trial.
- 2) The BSI-18 at the beginning of the screening period.
- 3) The IBS-QOL at the beginning, at 4 weeks and end of treatment.
- 4) The Nepean Dyspepsia Index at the beginning, 4 weeks and end of treatment as well as during the mail-in/phone call visits. BDQ (Bowel Disease Questionnaire) at screening.

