#### Drug, Dose and Duration Rationale

Mesalamine with MMX (Multi Matrix System) technology (Lialda®) will be used for this study. This is a novel oral, high strength (1.2 gm/tablet) formulation of 5-ASA designed for once or twice daily administration. Lialda has been shown to be well tolerated for the treatment of mild to moderate ulcerative colitis. Previous studies have shown that clinical and endoscopic remission with 2.4 and 4.8 gm/ day was similar. Therefore the 2.4gm once daily dose will be used for this study. A placebo capsule will be provided by the makers of Lialda, Shire Pharmaceuticals, Inc. All study medication will be stored and dispensed at the University of Utah and VA pharmacies.

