#### Time Line

##### *Location of Study*

This study will be performed at the University of Utah Hospital and Clinics and the VA Medical Center.

*Time Table of study:* Approximately 1 Years from the start of patient recruitment

Subject recruitment will start immediately upon IRB approval and continue throughout the duration of the study. We estimate that 50% of recruited patients will qualify for enrollment. Sixty-eight patients with diarrhea-predominant or mixed IBS (with diarrhea as predominant symptom) will be enrolled at the rate of 1-2 per week. The estimated dropout rate is 10%, leaving 64 patients to study. This population will include but not be limited to returned missionaries. We have previously worked with missionaries who have high prevalence of PI-IBS.

*Study visits* (Table 1. Figure 1.)

First visit:

Orientation to the study and informed Consent

Inclusion/Exclusion check

History and physical examination,

Questionnaires: BDQ, IBS-QOL, BSI-18, BSS, Nepean Dyspepsia Index (NDI)

Blood and stool tests (not repeated if done in past 6 months unless there has been an alteration in the symptoms)

Collection of stool sample for storage (if consent is given)

Urine pregnancy Test for women of child bearing potential

Instructions to complete 2 week stool diary during 8-week run in period

Second visit:

Flexible sigmoidoscopy/ colonoscopy with biopsy, if indicated (not repeated if performed during last 5 years, results within normal limits and no change in symptoms)

Third visit

Subjects will be randomly assigned to either two Lialda 1.2gm tablets daily or two placebo tablets daily according to a block randomization schedule generated by the statistician. Medicines will be provided by and dispensed at the Pharmacy. Medication may be mailed at patients' convenience and they will be informed on dosing and storage of medication by telephone.

Mail-in/ telephone visit

Patients will be asked to fill BSS IBS-QOL and NDI at week 4 of the 8 week treatment either by mail or on telephone.

Fourth visit

End of treatment- Questionnaires-BSS, IBS-QOL, and NDI and physical examination

Study drug count

Return all unused study drug and the study drug bottle(s)

**Standard of Care vs. Research-Related Procedures:** all procedures for this study are research-related.

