## **STATISTICAL METHODS, DATA ANALYSIS AND INTERPRETATION:**

### **Sample Size**

The sample size for this trial is based on primary end-point of overall improvement in BSS. A previous IBS treatment trial reported baseline BSS of  $183 \pm 65$ . To detect 25% change in BSS, 32 patients in each group will provide 80% power using two-sided alpha 0.05 comparisons. Assuming 5% drop out rate, we would require a total of 68 patients ( $n=34$  in each group). Assuming proportional estimates for the individual symptoms of IBS, a similar power will be achieved with this sample size.

The Lialda treated group will be compared to the placebo group on improvement in the BBS global symptoms of IBS (continuous scale, range 0 to 400) and BBS individual symptoms of IBS (continuous scales, range 0 to 100). Given the repeated measurements on continuous outcomes, the data will be analyzed with mixed effects linear regression.

Primary analysis will be based on intention to treat. Exploratory analyses assessing "compliers" will also be reported. We will compare the results of placebo and Lialda treated group. The key comparisons between treatment arms will assess changes from baseline to end of treatment using parametric approaches such as the t- test and, when data is highly skewed, nonparametric approaches such as the Wilcoxon test. We note that it is feasible to construct confidence intervals as well as significance tests in the setting of nonparametric comparisons. For some of the secondary efficacy approaches, such as those with binary/ categorical outcomes, follow-up status will be compared between treatment arms using the chi-squared test of the Mantel-Haenszel chi-square for ordered categorical outcomes. Exact versions of these tests will be performed when cell sizes are excessively small.

In addition to the unadjusted primary analyses we will perform exploratory analyses which will use the logistic regression model for binary outcomes, and the linear regression model for continuous outcomes (transformations or categorization may be necessary for the cell count variables). We expect that psychological factors may affect the response to treatment and therefore will do pre-study psychological analysis and will control for them while evaluating response to treatment.

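### Two enrolling sites with separate pharmacies, but no stratification of randomization by site is described and no analysis includes a site term

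*Combined protocol and SAP*

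**What the plan says.** **Sites and drug supply.** The Study Procedures section states: "This study will be conducted at the University of Utah and the VA Medical Center". The Drug, Dose and Duration Rationale section states: "All study medication will be stored and dispensed at the University of Utah and VA pharmacies".

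**Allocation.** Under Time Line (Study visits, third visit), patients are assigned to mesalamine or placebo "according to a block randomization schedule generated by the statistician". The protocol does not give the block size, any stratification factor, the number of lists, or how assignments reach two pharmacies.

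**Analysis.** The Statistical Methods section plans a mixed effects linear regression of the BSS, arm comparisons of change from baseline by t-test or Wilcoxon test, and a linear mixed model for IBS-QOL. It calls the primary analyses unadjusted. The only covariates it names are psychological factors. Site is not mentioned. The Study Resources section says that data from both sites will be analysed together at the University.

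**The concern.** Permuted blocks keep the arms equal along the list. If two pharmacies draw from the same list, each block is split between sites in order of arrival, and nothing keeps the arms equal within the University or within the VA. One arm can then hold more VA patients than the other by chance.

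This matters only if symptom change differs between sites. There is some reason to allow for that. The University recruits through its travel clinic and mass e-mails to staff and students, so patient mix may not match that of the VA. The plan itself expects one patient characteristic, psychological factors, to affect response. Where sites do differ, an analysis without a site term leaves the between-site variation in the error, in a trial sized with almost no slack. Stratification cannot be added once the schedule is in use.

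**Working it through.** **1. The plan's own figure.** The inputs are from the Sample Size section: baseline BSS 183, SD 65, a 25% change, two-sided alpha 0.05 and 80% power.
- Target difference: 0.25 × 183 = 45.75 points.
- n per arm = 2 × (65 × (1.960 + 0.842) / 45.75)² = 31.7, rounded up to 32.
- Standard error at 32 per arm: 65 × √(2/32) = 16.25. Power = Φ(45.75/16.25 − 1.960) = 80.4%.
- 64/0.95 = 67.4, so 68 in total.

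The stated result, "32 patients in each group will provide 80% power using two-sided alpha 0.05 comparisons", is reproduced. The margin above 80% is 0.4 points.

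**2. Inputs the documents do not give.** The VA share p and the between-site difference in outcome g (in within-site SDs) are assumptions, shown as ranges below. As in the plan, 65 is taken as the SD of the outcome.

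**3. Chance imbalance if one list is shared.** Fix the arms at 34 and 34. The number of VA patients on mesalamine is then hypergeometric. The shift in the treatment contrast is (difference in VA share between arms) × g × 65. With g = 0.5, a site difference of 32.5 points:

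| VA patients of 68 | 95% range on mesalamine | Limit of shift (BSS points) | As % of 45.75 | Mean absolute shift |
|---|---|---|---|---|
| 12 | 3–9 | 6/34 × 32.5 = 5.7 | 12.5% | 2.3 |
| 17 | 5–12 | 7/34 × 32.5 = 6.7 | 14.6% | 2.8 |
| 24 | 8–16 | 8/34 × 32.5 = 7.6 | 16.7% | 3.0 |

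For scale, the standard error with 34 per arm is 65 × √(2/34) = 15.8, so a 6.7-point shift is about 0.4 standard errors.

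Simulating one list of 68 in blocks of 4 (20,000 runs), the arms' VA shares differ by at least 10 percentage points in about 11%, 37%, 43% and 47% of trials at VA shares of 10%, 20%, 30% and 50%. They differ by at least 20 points in about 1%, 3%, 6% and 9%.

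**4. Power without a site term.** If 65 is the within-site SD, omitting site multiplies the variance by 1 + p(1 − p)g². At 32 per arm, with 80.4% as the reference:

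| VA share p | g | Variance factor | Power | Loss (points) |
|---|---|---|---|---|
| 10% | 0.5 | 1.0225 | 79.5% | 0.9 |
| 30% | 0.5 | 1.0525 | 78.4% | 2.0 |
| 50% | 0.5 | 1.0625 | 78.0% | 2.4 |
| 10% | 1 | 1.09 | 76.9% | 3.5 |
| 30% | 1 | 1.21 | 72.6% | 7.8 |
| 50% | 1 | 1.25 | 71.2% | 9.2 |

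If g = 0 the factor is 1 and nothing is lost. If 65 is instead the total SD, site differences included, planned power stays at 80.4%, and adjusting for site raises it to 81–83% (g = 0.5) or 84–88% (g = 1).

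**5. Type I error and the cost of adjusting.** In simulations of 64 patients (20,000 runs, blocks of 4, one list), the unadjusted t-test rejected a true null in 4.5–5.2% of trials. At a 30% VA share, unadjusted versus site-adjusted power was 79.4% v 78.6% (g = 0), 76.9% v 78.4% (g = 0.5) and 70.9% v 78.7% (g = 1). At a 10% share and g = 0.5 there was no gain (78.0% v 78.0%). With no site difference, adjusting cost 0.5–0.9 points across shares of 10–50%.

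**The case against.** The other side has four arguments, and most of them stand in part.

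- **One shared list is not stated.** A reader might infer from the singular wording that both sites draw on one unstratified schedule. The text does not say so, and a schedule with a section for each site would fit it equally well. What stands against the plan is that it does not say which applies, and two pharmacies cannot run the allocation from this text alone.
- **Different site populations are not documented.** A reader might infer them from the recruitment sources. However, VA patients are never described, the same types of clinic are named at both institutions, one set of eligibility criteria applies, and no outcome by site is reported. The site difference is therefore an assumption, and zero is within its range.
- **The unadjusted comparison is valid.** A reader might infer that site imbalance biases the result or makes the stated sample size wrong. It does neither. Chance imbalance is already reflected in the unadjusted standard error, type I error stays near 5%, and the 32 per group reproduces.
- **The study is small and preliminary.** It is meant to inform a larger trial, and leaving site out of the design is a choice rather than an error. With a small VA share the gain is slight.

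These arguments limit the size of the point. They do not defend the silence on how allocation runs across sites, and they give no reason to decline a change that costs so little.

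**Conclusion.** The point holds as a gap in the description and a modest loss of efficiency. Randomization is not described as stratified by site, and site is in no analysis, although there are two sites and two pharmacies.

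The consequence is conditional. It needs a site difference in outcome, and for the imbalance part also a shared list. At an assumed 0.5 SD difference, a typical chance shift is 2.3–3.0 BSS points and the 95% limit is 5.7–7.6, against the target of 45.75. For a VA share of 10–50%, with 65 as the within-site SD, the power lost is about 1–2.5 points at 0.5 SD and 3.5–9 points at 1 SD. It is zero if the sites do not differ. There is no systematic bias, so this is an inexpensive improvement and not a flaw that invalidates the trial.

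**What to change.** - **Time Line, third visit:** state that the statistician generates separate permuted-block schedules for the University and the VA, give the block sizes (in a document withheld from enrolling staff, if preferred), and say how each pharmacy receives its own list.
- **Statistical Methods:** include site as a fixed effect in the primary BSS mixed model and in the IBS-QOL mixed model. The unadjusted comparison can stay as a supporting analysis.

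The cost is one extra list and 1 degree of freedom. If the sites do not differ, it is under about 1 point of power. No patients, visits or measurements are added. The stratification has to be in place before the schedule is generated. The site term can still be specified at any time before unblinding.

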#### **Study End-points**

Primary: Improvement in self reported overall Bowel Symptom Scores (BSS) after 8 weeks of treatment will be used as the primary endpoint.

Secondary:

- 1) Change in specific bowel symptoms: bowel frequency, bowel consistency, abdominal pain, urgency, and bloating after 8 weeks treatment.
- 2) IBS-QOL at end of treatment

*Definition of a Responder:* Patient who report at least 50% of the weeks of treatment with satisfactory relief (30% or more reduction in symptom) will be designated as responders.

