##### *Bowel Symptom Scale (BSS)*

BSS is a validated IBS outcome measure which consists of 100-mm visual analog scales related to each symptom of IBS (pain/ discomfort, bloating, constipation, diarrhea) and an overall severity scale. All questions contribute equally to the total score, which ranges from 0-400. Similarly reflux disease questionnaire (RDQ) measures change in upper gastrointestinal symptoms before and after treatment.

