#### Assessment of Compliance

Every subject will be evaluated so that they are at least 80% compliant for continuous dosing of medication by pill count. Adverse reactions will be assessed. Patients will be called by the study coordinator every two weeks during the 8 week treatment period to check for medication compliance.

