We note that IBS-QOL will be collected at 4-week intervals. Therefore, approaches incorporating repeated measures, notably the linear mixed model, will be implemented to assess and quantify trends (e.g., a linear divergence between treatment arms) over time. These approaches also allow the inclusion of available data from patients who drop out in the middle of the study in the analysis. We are aware, however, that the dropout pattern in this study may not be the "Missing at Random" pattern required for such available-data models to yield valid inference. We will examine and report characteristics of study completers versus dropouts, to obtain some empirical evidence for or against this missingness assumption.

We are familiar with imputation approaches, and will implement these when appropriate. Simplistic approaches such as substituting each subject's "worst" value, or the "worst" value observed for any subject, for missing values may shed light on the robustness of any significant findings to missing data. However, such substitution approaches are not useful for formal statistical inference.

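### The week-4 BSS may be taken by telephone although the scale is a marked 100-mm line, and the plan gives no telephone version and no record of mode

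*Combined protocol and SAP*

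**What the plan says.** The section on the Bowel Symptom Scale gives the format: "BSS is a validated IBS outcome measure which consists of 100-mm visual analog scales related to each symptom of IBS". It adds an overall severity scale and a total running from 0 to 400.

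The Treatment Schedule sets three administrations: "The Bowel Symptom Scale (BSS) at the beginning, at 4 weeks and at the end of the study period". Under Study visits, the Mail-in/telephone entry says that patients will be "asked to fill BSS IBS-QOL and NDI at week 4 of the 8 week treatment either by mail or on telephone". The Study Procedures table agrees: the week-4 column is a mail/telephone visit with the BSS ticked, while Visit 1 and Visit 4 (week 8) are in person.

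The primary endpoint is defined at week 8: "Improvement in self reported overall Bowel Symptom Scores (BSS) after 8 weeks of treatment will be used as the primary endpoint". For analysis, the Sample Size section says "Given the repeated measurements on continuous outcomes, the data will be analyzed with mixed effects linear regression", and further on, "The key comparisons between treatment arms will assess changes from baseline to end of treatment".

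No section describes how a BSS is scored by telephone, tells the patient to have a form at hand during the call, asks staff to record the mode, or plans an adjustment or sensitivity analysis for mode.

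**The concern.** A visual analog scale is answered by marking a line, and the mark is then measured. Without a form in front of the patient, a telephone answer has to be a spoken number, which is a different response format. The protocol calls the line-based scale validated and says nothing about a spoken one. As written, week 4 could hold marked lines for some patients and spoken numbers for others, and nobody could later tell which is which.

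Week 4 is one of only two on-treatment BSS measurements, and the plan puts the repeated measurements into a mixed model. For a patient who leaves between weeks 4 and 8, it is the only on-treatment BSS the model has. A mode difference could add noise at week 4 and displace the time course. If telephone use differs between arms, it could also bias the week-4 difference. If mode is not recorded, none of this can be examined afterwards.

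**Working it through.** **Inputs from the documents.** Baseline BSS 183, SD 65; target a 25% change; 32 evaluable per arm; 80% power; two-sided alpha 0.05; dropout 5%; total 68 (all from Sample Size). The Time Line section gives dropout as 10%. BSS total 0 to 400, taken here as four 100-mm scales.

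**Reproducing the plan's figure.** Target difference = 0.25 × 183 = 45.75 points. The normal-approximation formula n = 2(1.960 + 0.842)² × 65² / 45.75² gives 31.7, so 32 per arm, with power 0.804. The t-test version gives 32.7 per arm and power 0.791 at 32. Allowing for 5% dropout, 32 / 0.95 = 33.7, so 34 per arm and 68 in total. The plan's figures reproduce. The point does not depend on them, but they set the yardstick of 45.75.

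**Assumptions.** The documents give neither a mode effect nor a telephone share. I assume a shift of 3 to 5 mm per scale, in the same direction on all four, so 4 × 3 = 12 to 4 × 5 = 20 points on the total. I assume a telephone share of 25% to 50% and, for bias, a difference in share between arms of 20 percentage points.

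**1. Completers, baseline to week 8.** Week 4 does not enter this change. In a straight-line fit to complete data at weeks 0, 4 and 8, the slope weights are −0.125, 0 and +0.125, so week 4 has no weight there either.

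**2. Equal telephone share in both arms.** The shift cancels in the between-arm difference. It moves the week-4 mean in both arms by share × shift, from 0.25 × 12 = 3 to 0.50 × 20 = 10 points, which distorts the time course. The week-4 SD becomes √(65² + p(1 − p)m²), where p is the share and m the shift. With p = 0.5 and m = 20 this is √(4225 + 100) = 65.8, and the power of a week-4 contrast for 45.75 points falls from 0.804 to 0.795.

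**3. Unequal telephone share.** Between-arm bias at week 4 = shift × difference in share:

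| Shift (points) | Week-4 bias | % of 45.75 | Bias in an average of weeks 4 and 8 |
|---|---|---|---|
| 12 | 0.20 × 12 = 2.4 | 5% | 1.2 |
| 20 | 0.20 × 20 = 4.0 | 9% | 2.0 |

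**4. Through dropouts.** As an extreme case, suppose every dropout in one arm leaves after week 4 and was telephoned, no dropout in the other arm was, and week 4 stands in for week 8 at full weight. The arm mean then moves by dropout rate × shift: from 0.05 × 12 = 0.6 to 0.10 × 20 = 2.0 points, or 1% to 4% of target. A mixed model would give week 4 less than full weight.

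**Stress check.** Doubling the upper shift to 40 points gives a week-4 bias of 0.20 × 40 = 8 points (17% of target). With half the patients telephoned, the week-4 SD is 68.0 and week-4 power 0.768.

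**The case against.** The strongest reply is that the primary result hardly depends on week 4. The endpoint is set at week 8, the key comparison runs from baseline to end of treatment, and both of those scores are collected in person. That stands, and it limits the point to the mixed model, the time course and the patients who leave after week 4.

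A second reply is that the plan is silent here rather than wrong: a patient might mark a form at home and read out the result. That is possible, so the documents do not prove that two different instruments will be used. But nothing provides for such a form, and a value read out by the patient is still not a line measured by staff.

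A reader might infer more than the documents support:

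- **A shift of 12 to 20 points is 26% to 44% of the target effect.** This divides an assumed within-patient shift by a between-arm difference. A shift common to both arms cancels; only the difference in telephone share carries through.
- **The primary endpoint is no longer self-reported.** A spoken answer is still the patient's own report, and the primary time point is in person.
- **The person asking about pills would also take the scores.** The protocol says "Patients will be called by the study coordinator every two weeks during the 8 week treatment period to check for medication compliance", so a call probably falls near week 4, but it does not say who collects the questionnaires. The trial is also double-blind.
- **The stated dropout plan is written for the BSS.** The sentence "These approaches also allow the inclusion of available data from patients who drop out in the middle of the study" follows a remark about IBS-QOL, which is a 34-item questionnaire and is not described as a visual analog scale. The BSS is affected because a mixed model is separately named for it and would use whatever data are available.

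**Conclusion.** The gap is real and modest. The plan allows the week-4 BSS to be collected in two response formats without showing that they are equivalent and without recording which was used. The completers' baseline-to-week-8 contrast is untouched.

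Under an assumed 12 to 20 point shift and a 20-percentage-point difference in telephone share, the week-4 difference would be biased by about 2.4 to 4 points, 5% to 9% of the 45.75-point target. An analysis averaging weeks 4 and 8 would carry half of that. The route through dropouts is worth at most about 2 points, and the loss of week-4 power is negligible. All of these scale directly with the assumed shift and share, neither of which the documents give. The textual facts are certain; the size is not. The case for acting is that the change costs little and that an unrecorded mode cannot be recovered later.

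**What to change.** Amend the Mail-in/telephone visit entry and the Study Procedures table so that printed BSS forms go out with the study drug at Visit 3, whether that supply is handed over or mailed. The patient marks the lines at week 4 and mails the form back, and the telephone is used for reminders. The protocol already allows mail for both the medication and the week-4 questionnaires, so no new route is needed.

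If a BSS can be obtained only by telephone, keep it and record the mode. Report the mixed model with and without telephone BSS scores as a sensitivity analysis. Excluding these scores from the primary model outright would discard data from patients who are hard to reach, where the plan itself doubts that data are missing at random.

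IBS-QOL and NDI may stay by mail or telephone, with the mode recorded, since the visual-analog argument does not extend to them.

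The cost is a short amendment, printing and return postage, one extra field on the case report form, and possibly a few late or missing week-4 forms. Week 8 is unchanged.
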